3 INTRODUCTION, RATIONALE

Sudden cardiac death (SCD), defined as an unexpected death from a cardiac cause occurring within \leq 1 hour of the onset of symptoms, accounts for 300,000 to 400,000 deaths in the United States annually, or 5.6% of annual mortality.¹⁻³ SCD is most commonly caused by ventricular tachyarrhythmias, including ventricular tachycardia (VT). Several therapies exist for the prevention of VT, including implantable cardioverter-defibrillator therapy (ICD), anti-arrhythmic drug therapy (AAD), and the use of catheter based ablation.

Current guidelines recommend the use of implantable cardioverter-defibrillator (ICD) as therapy to prevent SCD in patients who have survived a prior cardiac arrest due to unstable VT or who have had a previous episode of spontaneous sustained VT.⁴ Several trials have demonstrated the efficacy of ICD therapy in preventing SCD.^{5,6} The MADIT II trial, a randomized trial of patients with prior myocardial infarction and left ventricular ejection fraction \leq 30%, demonstrated a 31%

reduction in the relative risk of death in the defibrillator group.⁶ However, ICD therapy does not prevent VT, and a significant proportion of patients may still experience appropriate shocks. In the Antiarrhythmics Versus Implantable Defibrillators (AVID) Trial, 60% of patients had ≥ 1 appropriate ICD therapy for VT/VF during follow-up (31±13 months), and the first arrhythmia resulting in a shock during follow up was frequently identified as VT (63%). Unfortunately, these ICD shocks are associated with both a significant reduction in quality of life and increased mortality. In a study examining quality of life in patients who had received ICD shocks, at 5.5 years post ICD implantation 19% of patients demonstrated signs of post-traumatic stress disorder.⁷ In the MADIT II trial, patients who experienced VT/VF had an increased risk of death, with a hazard ratio of 2.5.⁶ Thus, while ICDs have a clear overall mortality benefit in patients with a reduced ejection fraction, the ICD shocks themselves clearly reduce the quality-of-life of these patients and may have a negative impact on their longevity.

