10. STATISTICAL ANALYSIS PLAN

10.1 STUDY DESIGN

This is a prospective, multi-center, parallel groups, single-blinded, randomized clinical trial. Patients with ischemic or non-ischemic ventricular dysfunction who are to receive an ICD for either 1) secondary prevention, or 2) primary prevention + inducible VT by programmed ventricular stimulation at the time of ICD implantation will be randomly assigned using a 1:1 allocation to treatment to ICD alone or ICD + RSDN. Randomization will be stratified by center.

Our study will include U.S. as well as European sites. We do not anticipate that the two populations will be different. We expect the U.S. population to include 85% Caucasian and the EU population to be 100% Caucasian.

Before conducting the primary analysis we will compare the two populations with respect to baseline characteristics. If a difference is found, the region will be included in all our models as a covariate. We do not anticipate that the treatment effect will be differential in EU and the U.S. This hypothesis will be formally tested using an interaction term in our models.

10.2 PRIMARY OBJECTIVES:

The primary objective is to evaluate the effectiveness of RSDN in the primary prevention of ICD therapy in patients with ischemic or non-ischemic ventricular dysfunction who are to receive an

ICD for either i) secondary prevention, or ii) primary prevention + inducible VT by programmed ventricular stimulation at the time of ICD implantation.

10.3 PRIMARY EFFECTIVENESS ENDPOINT:

The primary effectiveness endpoint is time to first event requiring any ICD therapy (appropriate or inappropriate) or Incessant VT (VT occurring below the ICD rate cut-off); this will be assessed in the on-treatment patient cohort. An event requiring ICD therapy is defined as an anti-tachycardia pacing (ATP) or shock therapy. The null hypothesis of interest is that there will be no difference between the two treatment arms in the time to first event requiring any ICD therapy (appropriate or inappropriate) or Incessant VT in patients randomized to ICD implantation with a single renal sympathetic denervation procedure compared to patients randomized to ICD implantation alone.

10.4 PRIMARY SAFETY OBJECTIVE:

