10.6 POWER AND SAMPLE SIZE

Power for this study was determined based on the following operating characteristics: (a) two sided type I error fixed at 0.0492, assuming one interim analysis, (b) 85% power, (c) minimum follow-up of 18 months, (d) 18-months event rate in the ICD alone group of 19% (e) expected 18-month relative rate reduction in the ICD + RSDN group of $\geq 40\%$, accrual period of 48 months and non-uniform accrual.

Under the above assumptions it is estimated that 70 events (or 462 patients) will be required to detect a relative decrease in the relative event rate reduction requiring any ICD therapy $\geq 40\%$ in the ICD + RSDN compared to the ICD alone group (19% vs. 11.4%) (Lachin, 1981).

Lost to Follow Up: The term "lost to follow-up" is used to define an individual who has withdrawn consent to be in the study or who can no longer be located or assessed. Such individuals represent those for whom primary outcome assessment is no longer possible. Since the primary outcome will be assessed by interrogating the ICD and since patients come back to

the hospital for regular check we do not anticipate a high rate of lost to follow-up. The estimated sample size accounts for 5% attrition due to withdrawal of consent.

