10.8 STATISTICAL ANALYSIS

The primary analysis will be an intent-to-treat analysis that will include all randomized participants regardless of treatment actually received or follow-up schedule.

Point Estimation and Interval Estimation: We will report maximum likelihood estimates for point estimation. For routine reporting, two-sided 95% confidence intervals for all parameters will be prepared.

Disposition of Participants and Baseline Comparisons: Summaries of all participants randomized and the number who complete visits at 30-days, and every 6 months after the day of randomization will be provided for each treatment group. The treatment groups will be compared at baseline with respect to demographics, baseline measurements related to efficacy and baseline measurements related to safety.

Univariate Analysis: All outcome measures will be described in a univariate analysis. For continuous variables means and standard deviations will be calculated. For discrete and dichotomous variables we will use contingency tables.

Analysis of Primary Endpoint: The primary endpoint of this study is defined time to first event requiring any ICD therapy (appropriate or inappropriate) or Incessant VT (VT occurring below the ICD rate cut-off); this will be assessed in the on-treatment patient cohort. An event requiring ICD therapy is defined as an anti-tachycardia pacing (ATP) or shock therapy. Time to event will be estimated using Kaplan-Meier curves. Survival time will be defined as the time (in months) between randomization and the occurrence of first ICD therapy. To compare the ICD+ RSDN arm with the ICD alone arm we will use a stratified log-rank statistic (using the stratification variables from the randomization procedure). A Cox proportional hazards model with treatment and other important prognostic factors as covariates will be used for the multivariate analysis of the times to first ICD therapy. Risk ratios and their 95% confidence intervals will be computed. Patients will be included in the analysis as censored if they are alive and free of ICD events at the end of the 18-month follow-up period. Although we do not anticipate interactions between treatment and stratification factors, formal tests for interactions will be assessed using proportional hazards models. A formal test of proportional hazards will assess the significance of

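### The primary-endpoint curves have no rule for death before first ICD therapy; if such deaths are censored, one minus Kaplan-Meier overstates each arm's actual event probability

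*Combined protocol and SAP*

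**What the plan says.** The primary endpoint (sections 5.1, 10.3 and 10.8) is time to first ICD therapy, meaning anti-tachycardia pacing or shock, or incessant VT. Death is not a component. All-cause mortality is a separate secondary endpoint (sections 5.2 and 10.5).

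For the analysis, section 10.8 states: "Time to event will be estimated using Kaplan-Meier curves". The arms are compared by a stratified log-rank test, and a Cox model gives risk ratios with 95% confidence intervals. Two censoring rules appear in section 10.8:

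- Patients are "censored if they are alive and free of ICD events at the end of the 18-month follow-up period".
- Patients who withdraw consent without an event are censored at withdrawal (Missing Data paragraph).

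Neither rule covers a patient who dies without an event. Section 10.6 defines loss to follow-up by withdrawn consent or inability to locate or assess the patient, and its 5% attrition allowance is for withdrawal only. No cumulative incidence function or other competing-risk method is named. For secondary endpoints section 10.8 names mixed models and GEE, so mortality has no time-to-event method either.

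The design effect in section 10.6 is expressed in absolute rates: "18-months event rate in the ICD alone group of 19"% against 11.4% with RSDN.

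**The concern.** A patient who dies event-free can no longer receive ICD therapy, so death is a competing event. Censoring at death treats that patient as someone who could still have had the event later. One minus the Kaplan-Meier curve then estimates the risk in a hypothetical setting without death, and this is higher than the share of patients who will have ICD therapy. Some deaths must be expected: patients have structural heart disease and an ICD indication, and the exclusions tied most directly to prognosis are NYHA class IV and life expectancy under one year (section 6.2).

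Two things are at stake. First, the absolute event rates and the risk difference, which is how section 10.6 frames the expected benefit, would not be actual probabilities. Second, because the handling of event-free deaths is unstated, two analysts could treat them differently and both comply with the plan.

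**Working it through.** **Inputs from section 10.6.** Event rate at 18 months: 19% control, 11.4% RSDN. Sample size 462, 231 per arm.

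**The plan's own figures.** 19% x (1 - 0.40) = 11.4%. Expected events by 18 months with no deaths: 231 x (0.19 + 0.114) = 70.2, which matches the planned 70. (Whether 70 events carry the stated 85% power is a separate question.)

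**Assumptions not in the documents.** Constant hazards; death independent of ICD therapy; mortality of 5% to 15% per year.

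**Hazards per month.**
- Control: l0 = -ln(0.81)/18 = 0.01171.
- RSDN: l1 = -ln(0.886)/18 = 0.00672.
- Death: m = -ln(1 - annual mortality)/12 = 0.00427 at 5%, 0.00878 at 10%, 0.01354 at 15%.

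**Formulas.** With deaths censored, 1-KM at time T estimates 1 - exp(-l x T). The actual probability of the event is the cumulative incidence, l/(l+m) x [1 - exp(-(l+m) x T)].

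**Example: control, 18 months, 5% per year.** l0 + m = 0.01598. The share still alive and event-free is 0.81 x 0.95^1.5 = 0.81 x 0.9259 = 0.7500. Cumulative incidence = (0.01171/0.01598) x (1 - 0.7500) = 0.7325 x 0.2500 = 18.3%.

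**18 months, equal mortality in both arms**

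| Mortality per year | Control | RSDN | Difference (points) |
|---|---|---|---|
| 1-KM, any mortality | 19.0% | 11.4% | 7.6 |
| Cumulative incidence, 5% | 18.3% | 11.0% | 7.3 |
| Cumulative incidence, 10% | 17.6% | 10.6% | 7.1 |
| Cumulative incidence, 15% | 16.9% | 10.1% | 6.8 |

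The control rate is 0.7 to 2.1 points too high, and the difference 0.3 to 0.8 points too large. If 5% to 15% is instead taken as mortality over the whole 18 months, the control cumulative incidence is 18.5% to 17.6% and the difference 7.4 to 7.1 points.

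**18 months, unequal mortality**
- 5% per year control, 15% RSDN: 18.3% - 10.1% = 8.2 points. 1-KM gives 7.6, so it understates the difference.
- 15% per year control, 5% RSDN: 16.9% - 11.0% = 6.0 points from unrounded values. 1-KM overstates the difference.

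**Effect on the primary test.** The log-rank test was simulated under no treatment effect with deaths censored (6,000 runs, 462 patients, 18 months, mortality of 5% to 15% over 18 months, equal or unequal between arms). Type I error was 0.045 to 0.050 against the nominal 0.0492; the same simulation without deaths gave 0.056. Deaths therefore do not inflate it. They do remove some events: 70.2 expected by 18 months becomes 68.5 to 65.0 with 5% to 15% mortality over that period. That is a loss of information and does not bias the test.

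**The case against.** The strongest reply is that this touches only a descriptive estimate. The planned inference is a log-rank test and a Cox model, no absolute risk difference is a declared estimand, and 1-KM with deaths censored is a recognised summary of net risk. Mortality is also visible elsewhere: it is a secondary endpoint, and the DSMB reviews it every six months (section 9.3.3). All of this stands and limits the weight of the point. It does not remove the missing rule for event-free deaths, and it does not make 1-KM the actual probability of ICD therapy.

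Four stronger readings are tempting but lack support:

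- **That the plan will overstate the absolute benefit.** This follows when mortality is equal in both arms. The unequal-mortality cases above show that it can reverse.
- **That the rationale proves that deaths are informative censoring.** Section 3 says that in MADIT II "patients who experienced VT/VF had an increased risk of death, with a hazard ratio of 2.5". That concerns death after VT/VF. Here, VT/VF treated by the ICD is itself the primary event, so those deaths follow the endpoint and do not compete with it.
- **That a mortality difference would shift the Kaplan-Meier curves unseen.** Under independent hazards, 1-KM contains no mortality term, so it does not move. The cumulative incidence curve is the one that moves: higher mortality with RSDN would make RSDN look better on it. It must therefore be read beside the curve for death.
- **That the error at 36 months is the relevant one.** The same formulas give 34.4% by 1-KM against 32.0-27.7% in the control arm, and a difference of 12.9 points against 12.1-10.5. Section 9.2.1 allows follow-up to 36 months, but section 10.8 censors event-free patients at 18 months, and no section says that 36-month rates will be reported.

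The upper mortality figure can also be challenged. At 15% per year, 1 - 0.85^1.5 = 22% would die by 18 months if no other event intervened, and the documents neither support nor rule out that level.

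**Conclusion.** The point holds as a matter of estimation and reporting. Death precludes the primary endpoint, is outside it, and has no stated handling. If event-free deaths are censored, 1-KM overstates each arm's actual event probability. For an assumed 5-15% annual mortality, independent of ICD therapy and with constant hazards, the 18-month control rate is 19.0% against 18.3-16.9%. With equal mortality, the risk difference is 7.6 points against about 7.3-6.8. With unequal mortality, the direction of the error in the difference is not fixed.

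The size at 18 months is modest, and no figure specific to this population can be derived from the documents. A reader might infer that the primary test is compromised. It is not: the log-rank test and Cox model compare cause-specific hazards and remain valid with deaths censored.

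**What to change.** In section 10.8:

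1. State that patients who die without a primary event are censored at death in the log-rank and Cox analyses, and that these analyses therefore concern the cause-specific hazard.
2. Report Aalen-Johansen cumulative incidence by arm with death as a competing event, in place of or beside 1-KM.
3. Show the cumulative incidence of death by arm next to it, so that a lower ICD-therapy curve caused by higher mortality can be recognised.
4. Add a sensitivity analysis of time to ICD therapy, incessant VT or death from any cause.

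This needs no new patients, visits or data, because mortality is already a secondary endpoint. The cost is a little extra analysis and slightly lower reported event rates. The primary test and its 0.0492 level do not change.

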10.7 INTERIM MONITORING GUIDELINES

The objectives of interim monitoring are to (1) monitor for safety, (2) track participant accrual rates, and (3) monitor the primary and secondary outcomes for early evidence of efficacy, harm or futility. To accomplish this, summaries of data quality, accrual, adherence, distribution of baseline factors, toxicity, study endpoints and other analyses as requested will be prepared for review by the Data Safety Monitoring Committee (DSMB).

The primary outcome of the trial, rate of first event requiring any ICD therapy, is the basis for formal interim analysis plan that follows. One interim analysis and one final analysis are planned for this trial, for a total of 2 analyses. These analyses will be performed when 0.5 and 1.0 fraction of the total number of events will have been observed. Since this study will have a target number of events of 70, we will have approximately 35 events observed between each analysis time.

We will use an alpha-spending O'Brien-Fleming sequential procedure as a guideline for decision making. At the interim analysis the value of the test statistic will be compared with the alpha spending function critical values. The two alpha values will be set at 0.0054 at the interim analysis and 0.0492 at the final analysis, which equate to critical values of 2.782 and 1.967 respectively. This monitoring plan maintains the overall type I error at 0.05, given one interim analysis.

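### Section 10.8 ends survival time at first ICD therapy, although the primary endpoint is first ICD therapy or incessant VT; the event definitions need to be aligned

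*Combined protocol and SAP*

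**What the plan says.** The Protocol Summary and sections 5.1, 10.3 and 10.8 all give the same composite primary endpoint: "time to first event requiring any ICD therapy (appropriate or inappropriate) or Incessant VT (VT occurring below the ICD rate cut-off". Sections 5.1 and 10.3 state the null hypothesis on that composite. The therapy component is limited to two device actions: "An event requiring ICD therapy is defined as an anti-tachycardia pacing (ATP) or shock therapy".

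A few sentences after restating the composite, the primary-endpoint paragraph of section 10.8 defines the time variable: "Survival time will be defined as the time (in months) between randomization and the occurrence of first ICD therapy". The Cox model is for the "multivariate analysis of the times to first ICD therapy". Patients are to be "censored if they are alive and free of ICD events at the end of the 18-month follow-up period".

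Section 10.7 says: "The primary outcome of the trial, rate of first event requiring any ICD therapy, is the basis for formal interim analysis plan that follows". Section 10.6 also describes the reduction to be detected in terms of ICD therapy, without incessant VT.

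**The concern.** Incessant VT is by definition below the ICD rate cut-off, and a therapy event is by definition ATP or shock. Incessant VT therefore does not enter the time variable under the name of ICD therapy. It is in the composite to capture what the therapy component does not, and the one sentence that tells the programmer when the clock stops leaves it out.

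Two analysts could follow this SAP in good faith and build different primary datasets. One would test the stated null hypothesis and the other a therapy-only hypothesis. The interim plan adds a second problem. The looks are set at 0.5 and 1.0 of 70 events. If the interim count follows the therapy-only wording of section 10.7 and the final count follows the composite, the 35-event trigger and the 70-event target refer to different outcomes.

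A choice of this kind, if left open, may end up being made after outcome data have been seen.

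**Working it through.** The point turns on which event ends the survival time, so the text decides it, not a calculation.

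**Step 1. The wording side by side**

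| Place | Event named | Incessant VT included? |
|---|---|---|
| Protocol Summary; 5.1; 10.3; opening of the primary-endpoint paragraph in 10.8 | ICD therapy or incessant VT | Yes |
| Null hypothesis, 5.1 and 10.3 | ICD therapy or incessant VT | Yes |
| 10.8, survival time | First ICD therapy | No |
| 10.8, Cox model | First ICD therapy | No |
| 10.8, censoring at 18 months | *ICD events* | Term undefined |
| 10.8, Missing Data | The primary event | Yes, by reference |
| 10.6, effect to be detected | ICD therapy | No |
| 10.7, interim outcome | ICD therapy | No |

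**Step 2. Three patients under the literal rule**

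- *ATP or shock only.* The event and its time are the same under either definition.
- *Incessant VT, then ATP or shock later.* The composite is reached at the incessant VT. The literal rule counts the patient, but at the later date.
- *Incessant VT only.* The composite is reached, but the literal rule gives no event time. If *ICD events* means therapies, the patient is censored as event-free. If it includes device-recorded VT, the patient is neither an event nor covered by the censoring rule.

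No later sentence in section 10.8 resolves the last two cases.

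**Step 3. Can the effect be sized?**

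Inputs from sections 10.6 and 10.7: 19% vs 11.4% at 18 months, 462 patients, 70 events, 85% power, "two sided type I error fixed at 0.0492, assuming one interim analysis", final critical value 1.967.

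The plan's event count is reproduced by 462 × (0.19 + 0.114)/2 = 70.2.

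The stated power is not reproduced from 70 events. With exponential times, HR = ln(1 − 0.114)/ln(1 − 0.19) = 0.574. Schoenfeld power is Φ(|ln HR| × √70/2 − 1.967) = Φ(0.554 × 8.367/2 − 1.967) = Φ(0.352) = 63.8%. By the same formula, 85% power needs 4 × (1.967 + 1.036)²/0.554², about 118 events. That shortfall is a separate matter, and this point does not rest on it. It does mean that 85% is not a usable baseline for a power loss.

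Let q be the share of composite events in patients who have incessant VT and never receive ATP or shock. The documents give no value for q, so the rows below are assumptions. They also assume that the 70 events are composite events, that the analysis date is fixed and that the HR is unchanged.

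| q (assumed) | Events counted, 70 × (1 − q) | Schoenfeld power, HR 0.574 |
|---|---|---|
| 0% | 70 | 63.8% |
| 5% | 66.5 | 61.6% |
| 10% | 63 | 59.2% |
| 20% | 56 | 54.3% |

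Even the direction is uncertain. If the 19% is already a therapy-only rate, as the wording of section 10.6 allows, restoring incessant VT would add events to the plan. And because section 10.7 times the analyses by event count, counting therapies only would first delay the looks; events would go uncounted only if follow-up ended first.

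**The case against.** The best defence is that first ICD therapy is shorthand. The paragraph that contains the sentence opens with the full composite, the Missing Data text refers to the primary event, and section 10.7 labels its phrase as the trial's primary outcome. That is a fair account of what was probably meant. It does not settle what will be coded, because the survival-time sentence is an explicit definition and the same narrowing recurs in the Cox, interim and sample-size text.

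The defence does stand against several stronger readings that a reader might infer:

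- *That the trial has decided to analyse a different endpoint.* The documents show an inconsistency, not a declared change.
- *That the censoring rule is therapy-only.* *ICD events* is undefined. Section 9.3.2 uses the same term for what the Clinical Events Committee adjudicates, and section 9.2.1 records VT episodes separately from ATP and shocks, so the term could include device-recorded VT.
- *That power falls from 85% to about 83% or 81%.* Those figures come from Φ(3.003 × √0.95 − 1.967) and Φ(3.003 × √0.90 − 1.967). They assume that 70 events deliver 85% power, that all 70 are composite events, and that 5% or 10% of them are lost. The first is contradicted by the check above and the documents support neither of the others.
- *That any brief slow run counts as an endpoint.* The word incessant is itself a qualifier. What is missing is an operational duration.
- *That slow VT would go unreported.* Total VT burden is a secondary endpoint and VT episodes are documented at every visit. The omission concerns the primary test.

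**Conclusion.** The point holds as an inconsistency that must be resolved before the primary analysis is programmed. Followed as written, section 10.8 leaves out a patient whose only event is incessant VT and dates late a patient whose incessant VT precedes therapy. The log-rank, Cox and interim analyses would then not test the composite null hypothesis of sections 5.1 and 10.3. This conclusion rests on the text alone and needs no assumption about how common incessant VT is.

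No single figure can be attached to it. The documents give neither an incessant-VT rate nor the basis of the 19%, so the table above is illustrative only. The absence of an operational duration for incessant VT is a secondary gap in detail.

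**What to change.** In section 10.8, define survival time as the time from randomization to the earlier of first ATP or shock or first incessant VT. Then:

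- name that same event for the Kaplan-Meier curves, the log-rank test and the Cox model;
- replace *ICD events* in the censoring rule with freedom from the primary event;
- use the same event in section 10.7 for the interim outcome and for the counts of 35 and 70;
- state in section 10.6 whether the 19% rate and the 70 events refer to the composite or to therapy alone.

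These are SAP wording changes. If the 19% proves to be therapy-only, the sample-size assumptions also need restating for the composite.

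Separately, the protocol endpoint definition should say how incessant VT is established, including its duration and how its onset is dated. Section 9.3.2 should say whether the Clinical Events Committee adjudicates it. That touches the Protocol Summary and section 5.1 as well, so it is a protocol clarification rather than an SAP edit. The criterion itself is for the investigators to set.

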6. STUDY SUBJECTS

6.1 INCLUSION CRITERIA

1. ≥ 18 years of age
2. Structural heart disease (post-MI, dilated cardiomyopathy, sarcoid myopathy, hypertrophic cardiomyopathy, etc.)
3. Planned for ICD implantation for:
 - i. Secondary prevention (e.g.: VT/VF arrest, sustained VT, syncope/inducible VT)
 - ii. Primary prevention + inducible MMVT during induction via ICD lead testing
 - iii. Primary prevention + fragmented QRS complex on 12-lead ECG
4. Accessibility of renal vasculature (determined by renal angiography)
5. Ability to understand the requirements of the study
6. Willingness to adhere to study restrictions and comply with all post-procedural follow-up requirements

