9.1.3 RENAL SYMPATHETIC ABLATION PROCEDURAL DETAILS

- Patients will be brought to the electrophysiology laboratory in a fasting state
- Patient sedation or anesthesia will be administered according to standard EP lab protocol.
- Vascular access will be achieved in standard fashion.
- IV heparinization will be instituted. Full systemic anticoagulation will be instituted as per standard hospital procedures to a target ACT of 250 seconds or greater (or equivalent level depending on testing system performed).
- Abdominal aortography will be performed to assess the renal arteries for the suitability of catheter-based renal denervation in all patients. For those patients in whom the angiogram demonstrates that the renal anatomy is inappropriate for the RSDN procedure (small renal arteries, extensive atherosclerosis, renal stenosis, etc.), the patient will be excluded from the study as a screen failure. The patient's baseline information will be collected but no further follow-up required (beyond assessing for any adverse events related to the procedure). If the renal arteries are deemed suitable for RSDN, the patient will then undergo randomization.
- Randomization will be done by permuted-block randomization centrally and will be stratified by site. Allocation concealment shall be maintained at all sites by the use of a web-based central randomization scheme. The operating physician controlling the delivery of ablative energy will be aware of the outcome. This approach has been selected to minimize (1) study bias and (2) placebo effect. The randomization schema will be blocked by size for each site.
- Catheter-based sympathetic renal denervation will be performed using the Vessix balloon ablation catheter for denervation (see image below). The operating physician will manipulate the ablation catheter into the renal arteries as per standard operating procedures.

- The Vessix catheter is available in various sizes, and can be used to treat arteries between 3 mm and 7 mm in diameter and more than 20 mm in length. Radiofrequency energy is delivered via 8 electrodes to four distinct sites within the artery in a bipolar fashion. As with other renal denervation procedures, this catheter delivers four lesions in the artery which are separated along the length of the artery and are also separated orthogonally in different planes (anterior, inferior, posterior, and superior).

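### The primary log-rank test is stratified by site only and ignores ICD indication, a likely prognostic factor known at baseline; prespecified adjustment would bring a small gain in power and protect against chance imbalance

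*Combined protocol and SAP*

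**What the plan says.** Section 6.1 admits three groups by ICD indication: "Secondary prevention (e.g.: VT/VF arrest, sustained VT, syncope/inducible VT"; primary prevention with inducible MMVT at lead testing; and primary prevention with a fragmented QRS complex. Section 9.1.3 states: "Randomization will be done by permuted-block randomization centrally and will be stratified by site", and section 10.1 agrees (by center).

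For the primary endpoint, section 10.8 says "we will use a stratified log-rank statistic (using the stratification variables from the randomization procedure", so site is the only factor in the test. The same section adds a Cox model with other important prognostic factors, calls it the multivariate analysis and does not list the factors. Section 10.1 would add region to the models only if the regions differ at baseline. Section 10.7 applies critical values of 2.782 (interim) and 1.967 (final) to the test statistic.

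**The concern.** Patients who have already had VT/VF and patients selected by inducibility or ECG may well have different rates of ICD therapy. If they do, a test that omits indication averages over the two risk levels. The estimated hazard ratio then moves slightly towards 1, some power is lost, and a chance imbalance in indication between the arms goes straight into the primary result.

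The planned Cox model does not close this gap. Its covariates can be chosen after the data are seen, and it does not decide the trial.

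**Working it through.** **1. The plan's own figures.** Section 10.6 gives "two sided type I error fixed at 0.0492, assuming one interim analysis", 85% power, and 18-month rates of 19% and 11.4%.

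- Exponential hazard ratio: ln(1 − 0.114)/ln(1 − 0.19) = ln 0.886/ln 0.81 = 0.574.
- Events by Schoenfeld's formula: 4(1.967 + 1.036)²/(ln 0.574)² = about 118. The plan states "70 events (or 462 patients) will be required".
- The 70 equals 462 × (19% + 11.4%)/2 = 462 × 15.2% = 70.2, the events expected by 18 months.
- Power with 70 events: Φ(√70/2 × 0.554 − 1.967) = Φ(0.35) = about 64%.

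The stated figure is not reproduced. That is a separate point, but it sets the power level at which adjustment operates.

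**2. Is indication prognostic?** No section gives event rates or case mix by indication. The fragmented-QRS relative risks in section 3 (1.71 and 2.20) concern mortality and sudden death and do not compare the three groups. One indirect comparison is possible. Section 3 cites a randomised ablation trial in patients implanted for spontaneous VT or VF, where 33% on ICD alone had therapy; the plan assumes 19% for its mixed population. The follow-up behind the 33% and this trial's case mix are not given, so I assume 18 to 24 months and 30% to 50% secondary prevention:

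- 18 months, 50%: the primary-prevention risk must be (19 − 0.5 × 33)/0.5 = 5%. The hazard ratio is ln 0.67/ln 0.95 = 7.8.
- 24 months, 30%: 33% at 24 months is 25.9% at 18 months. The primary-prevention risk is (19 − 0.3 × 25.9)/0.7 = 16.0%, and the hazard ratio is 1.7.

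The direction is plausible; the size is not pinned down.

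**3. Power.** Simulated trials had 462 patients, 15 sites (an assumption; section 7.1 allows up to 20), blocked 1:1 allocation by site, marginal 18-month rates of 19% and 11.4%, a binary indication, and a two-sided 0.0492 test. Both censoring rules are shown because section 10.8 censors at 18 months while section 9.2.1 follows patients for up to 36. The comparison is the planned site-stratified log-rank against a site-stratified Cox model (Wald test) with indication, 6,000 trials per row.

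| Assumed prognostic HR, high-risk share | Follow-up | Log-rank % | Cox % | Gain, points (SE) |
|---|---|---|---|---|
| 2, 50% | 18 mo | 61.37 | 61.43 | +0.07 (0.26) |
| 2, 50% | to 36 mo | 82.15 | 82.43 | +0.28 (0.24) |
| 3, 30% | 18 mo | 60.95 | 61.50 | +0.55 (0.35) |
| 3, 30% | to 36 mo | 81.42 | 84.00 | +2.58 (0.35) |
| 5, 30% | 18 mo | 60.95 | 64.53 | +3.58 (0.42) |
| 5, 30% | to 36 mo | 77.97 | 84.25 | +6.28 (0.42) |

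- With a weak or null factor (HR 1 to 1.5, 50% share, 3,000 trials), the same comparison changed power by −0.8 to +0.4 points.
- With a treatment HR of 0.574 within indication, HR 4 and a 50% share, power to 36 months rose from 78.3% to 82.0% (+3.7). The gain was about 1 point at 18 months.
- A further set over HR 1 to 4 gave −1.0 to +1.6 points (18 months) and −0.3 to +4.8 points (to 36 months).
- Stratifying the log-rank by site and indication together did worse: −1.05 and −0.67 points at HR 2, and −0.85 and +0.37 at HR 3. Indication is better entered as a covariate than as a stratum.

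**4. Attenuation.** With a true hazard ratio of 0.574, the median estimate moved from 0.584 to 0.576 (prognostic HR 2.5) and from 0.589 to 0.571 (HR 4).

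**5. Chance imbalance.** With 231 per arm and half secondary prevention, the between-arm difference in that share has SD √(0.25 × 2/231) = 4.7 points. A 1.96-SD difference is 9.1 points, that is 54.6% against 45.4%. The unadjusted hazard ratio then shifts by about (1 + 1.5 × 0.546)/(1 + 1.5 × 0.454) = 1.08 at HR 2.5, and (1 + 3 × 0.546)/(1 + 3 × 0.454) = 1.12 at HR 4, in either direction.

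**6. Type I error.** One null run (3,000 trials, prognostic HR 2, 18 months) gave 4.4% for the site-stratified log-rank and 4.1% for the adjusted Cox test, against a nominal 4.92%.

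**The case against.** A log-rank test stratified by the randomisation factors is conventional and valid, and randomisation already protects the type I error. The prognostic strengths above are assumptions. The endpoint also counts inappropriate therapy, which indication need not predict, so the true strength may be lower. Section 10.8 already plans baseline comparisons and a Cox model, and section 10.1 may add region. All of this stands, and it makes the point a refinement rather than an error. It does not answer the imbalance argument, because covariates that are unnamed and outside the primary test cannot protect the primary result.

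A reader might infer more: that indication is the main prognostic factor, and that adjusting for it recovers power at no cost. The documents support neither. They contain no hazard ratio by indication, and the 33% against 19% comparison mixes different populations. Nor is adjustment free. A weak factor costs a fraction of a point to about 1 point, the p-value rests on the Cox model, and the hazard ratio becomes conditional on indication.

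**Conclusion.** The primary test does omit a baseline factor that is likely to be prognostic, and no section names that factor for any adjusted analysis. The consequence is small. For a prognostic hazard ratio of 2 to 4, adjustment gains about 0 to 1.6 points of power with 18-month censoring and about 0.5 to 5 points with follow-up to 36 months. These limits are approximate: simulation error is a few tenths of a point, and at a 30% high-risk share the rows for 3 and 5 suggest that the 18-month gain at 4 could somewhat exceed 1.6. Gains are clearly larger only if the factor is very strong (about 5).

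The firmer reason to adjust is that a single prespecified model removes the effect of chance imbalance and the freedom to choose covariates. It does not rescue the sample size: even at a prognostic hazard ratio of 5, power with 18-month censoring reaches only about 65%.

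**What to change.** In section 10.8, define the primary comparison as a Cox model stratified by site, with treatment and ICD indication (secondary versus primary prevention) as covariates. State which Cox statistic supplies the p-value. In section 10.7, apply the existing critical values to that same statistic at the interim and final looks. Keep the site-stratified log-rank as a sensitivity analysis, and describe the reported hazard ratio as conditional on indication.

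Use two levels rather than three: a primary-prevention patient can be inducible and also have a fragmented QRS, and section 6.1 does not say how to classify such overlap. Fix the indication before randomisation and write down the rule for syncope with inducible VT, which section 6.1 lists under secondary prevention. At the least, name this variable in the Cox model already planned.

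The cost is SAP wording and a coding rule. Randomisation need not change, and indication is already established at eligibility. The price is the one set out above: up to about 1 point of power if indication is not prognostic, reliance on the Cox model, and a conditional hazard ratio.
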